#### **10.7.4. Reporting to Regulatory Authorities, Investigators, and Institutional Review Boards/Independent Ethics Committees**

The Sponsor will ensure that processes are in place for provision of SAEs and Expedited SAE reports (SUSARs) to regulatory authorities, Investigators, and Institutional Review Boards (IRBs)/Independent Ethics Committees (IECs) as required within the specified timelines.

The Sponsor will submit SAE and/or SUSAR reports to regulatory authorities and the Investigator as required. In the US, Investigators will report SAEs and SUSARs to their IRB in accordance with applicable SOPs and/or local reporting requirements. In Europe, the Sponsor or its designee will notify the IEC of any SUSARs. In regions/countries other than the US/Europe, reporting of events to IECs or local authorities will be performed by the Investigator/Sponsor or its designee and will be done in accordance with local procedures/regulations.

Investigators will forward copies of the IRB/IEC notification to the Sponsor or its designee, when applicable.

#### **10.8. Pregnancy Reporting**

Although not an AE in itself, exposure to study medication during pregnancy must be reported; therefore, all pregnancies in female patients will be recorded on the AE eCRF and the pregnancy reporting form. If a patient becomes pregnant during the study, study medication will be immediately discontinued, and pregnancy will be documented as the reason for study medication discontinuation. If a urine pregnancy test is positive, study medication will be immediately discontinued until a serum pregnancy test confirms the result.

If the Investigator suspects that a pregnancy was the result of an interaction between the study medication and the contraceptive method, in addition to the pregnancy, the study medication interaction will also be captured as a separate AE.

The Investigator will report any pregnancy associated with exposure to study medication from the time of first dose until at least 90 days after final study medication administration (including open-label sparsentan). When a site becomes aware that a patient is pregnant, they are to contact the Medical Monitor immediately (within 24 hours of the site becoming aware of the event), complete an initial Pregnancy Notification Form, and send the form by email to the SAE contact on the [Study Contact Information](#) page of this protocol or by fax to the number in the Investigator Site File.

Sites will contact patients monthly to confirm that the required pregnancy test has been performed and the results are negative. Female patients will be instructed to notify the Investigator immediately if they discover they are pregnant.

If the Investigator learns of a report of pregnancy after signing informed consent, the Investigator will complete the Pregnancy forms and submit them to the study contact on the Study Contact Information page of this protocol or by fax to the number in the Investigator Site File.

All pregnancies in female patients will be followed to outcome (ie, delivery, elective termination, spontaneous abortion). Infants should be followed for a minimum of 8 weeks. In certain cases, it may be necessary to follow-up on the long-term outcome of the AE using the pregnancy follow-up form. The Investigator will inform the patient that the Sponsor or its designee is required to gather information regarding the course and outcome of the pregnancy after exposure to the study medication. All study-related visits/contacts involving a known pregnancy will include pregnancy status assessment until pregnancy outcome is known. The Investigator should further obtain follow-up information no later than 1 month after the gestational period to obtain maternal/fetal/neonatal outcome and any other relevant information (after obtaining consent from the patient or the patient's partner). Upon obtaining pregnancy outcome, the Investigator will complete the Pregnancy Outcome form and submit it to the study contact on the Study Contact Information page of this protocol or by fax to the number in the Investigator Site File.

All information related to the pregnancy and its outcome will be assessed for the occurrence of an AE or SAE. Spontaneous abortions and stillbirths will always be reported as SAEs. Should an AE or SAE occur in the patient and the patient decides to continue in the study after permanently discontinuing study medication, the event will be processed per routine study guidelines. However, if the patient decides not to continue in the study, all AEs and SAEs will be documented and provided directly to the SAE contact on the Study Contact Information page of this protocol. Likewise, if the pregnancy results in the birth of a child and an AE or SAE occurs in the child, the data will be documented and provided directly to the SAE contact.

## **11. DATA COLLECTION, QUALITY ASSURANCE, AND MANAGEMENT**

### **11.1. Recording of Data**

The study will use eCRFs for data collection. The data will be entered by trained site personnel only. The Investigator is responsible for ensuring that all sections of each eCRF are completed promptly and correctly and that the data can be verified against source data.

AEs and medical history will be coded using MedDRA. Similarly, prior and concomitant medications and concomitant therapies will be coded using the World Health Organization Drug Dictionary.

### **11.2. Data Quality Assurance**

To ensure compliance with GCP and all applicable regulatory requirements, the Sponsor or its designee may conduct a quality assurance audit.

### **11.3. Data Management**

Data management will be performed by a qualified vendor under their SOPs. The Sponsor will provide oversight.

## 12. STATISTICAL METHODS AND PLANNED ANALYSES

### 12.1. General Considerations

The statistical principles applied in the design and planned analyses of this study are consistent with the ICH Guideline E9 (Statistical Principles for Clinical Trials).

All statistical analyses will be performed using Version 9.4 or later of Statistical Analysis System (SAS®). Data summaries will use descriptive statistics (n, mean, standard deviation, median, minimum, and maximum) for continuous variables and frequency and percentage for categorical and ordinal variables. Unless otherwise specified, endpoints will use the last pre-treatment value available prior to the first dose of study medication as baseline. All data collected will be included in patient data listings.

This section on statistical methodology outlines the principal statistical features pertaining to the analysis of the main efficacy endpoints and summary of safety data. A more detailed statistical analysis plan (SAP) will be prepared and finalized prior to the first planned efficacy analysis.

### 12.2. Sample Size Justification

The hypothesis to be tested relating to the change in proteinuria at Week 36 post-randomization is as follows:

$$H_0: \Delta = 0 \text{ versus } H_1: \Delta \neq 0$$

where  $\Delta$  is the true difference between sparsentan and irbesartan in the log change from baseline in proteinuria at Week 36. Based on data from the Leicester University Hospital Registry of IgA nephropathy patients (Leicester IgAN Patient Registry) in over 350 patients with IgAN (who were not treated with steroid therapy) provided by [name], together with proteinuria data published by Inker et al (Inker 2016), the standard deviation of the log change from baseline in proteinuria at Week 36 is estimated to be 0.92. A total of 280 randomized patients will, therefore, provide at least 90% power to test that the true relative treatment effect on proteinuria, sparsentan versus irbesartan, is at least 30%. Based on the data published in Inker, this degree of treatment effect is predicted to reflect a treatment effect on clinical outcomes (doubling of serum creatinine, ESRD, or death) with a hazard ratio of 0.36 and a 95% confidence interval (CI) of (0.22, 0.61). In addition, [name] patient registry database indicates that a 30% treatment effect on proteinuria at the patient level predicts a difference in the slope of eGFR decline that translates to an estimated difference in eGFR at 104 weeks (approximately 2 years) of 6.64 mL/min/1.73 m^2, with a 95% CI of (0.83, 12.44).

Approximately 380 patients will be required to detect an underlying treatment effect in the rate of change in eGFR over 110 weeks following the initiation of randomized therapy (eGFR total slope at 2 years) of 2.9 mL/min/1.73 m^2 per year with 90% power. In addition, approximately 380 patients provide 80% power to detect a smaller treatment effect on eGFR total slope at 2 years of 2.55 mL/min/1.73 m^2 per year. Consequently, approximately 380 patients provide more than 90% power to detect an underlying treatment effect in the rate of change in eGFR over 104 weeks following the initial acute effect of randomized therapy (eGFR chronic slope at 2 years) of 3.15 mL/min/1.73 m^2 per year. With this sample size, the observed annualized treatment difference to yield a p-value of <0.02 is 1.8 mL/min/1.73 m^2 per year. These sample size and power calculations follow the method described by Dupont (Dupont 1998), with

one-sided  $\alpha = 0.02$  and residual error of 5.8 mL/min/1.73 m^2 estimated from a random coefficient analysis of the Leicester University Hospital Registry. The projected treatment effects on the rate of change in eGFR were based on a meta-analysis of clinical studies in IgAN using the methodology presented by Inker ([Inker 2019](#)).

To investigate the safety and efficacy of SGLT2 inhibitors in combination with sparsentan on proteinuria in patients with IgAN, as compared to sparsentan alone, approximately 30 patients in each of the two treatment groups (total 60 patients) will be enrolled in the Sub-study. The sample size of the Sub-study is determined empirically without formal statistical assumptions.

### **12.3. Analysis Sets**

The analysis datasets to be used for the evaluation of efficacy and safety are defined in the following sections.

#### **12.3.1. Full Analysis Set**

All patients who are randomized and take at least 1 dose of randomized therapy will be included in the Full Analysis Set (FAS). Patients in the FAS will be analyzed according to randomized treatment assignment. If a patient is incorrectly stratified (ie, randomized according to an incorrect stratification), the patient will be analyzed under the randomized treatment for the stratum recorded in the IRT. All efficacy analyses for the double-blind period will be based on the FAS.

#### **12.3.2. Primary Analysis Set**

The Primary Analysis Set (PAS) is the subset of the FAS at the time of the data extraction for primary analysis. Patients in the PAS will be analyzed according to randomized treatment assignment. Primary analysis of proteinuria at Week 36 will be based on the PAS unless the study is fully enrolled in which case the FAS will be used.

#### **12.3.3. Per Protocol Analysis Set**

The Per Protocol (PP) Analysis Set is a subset of the FAS containing patients who meet study eligibility requirements and have no protocol deviations that might impact the assessment of efficacy measurements. Patients will be analyzed according to randomized treatment assignment. The PP Analysis Set will be used for sensitivity analyses relating to efficacy. The type of protocol deviations governing exclusion from the PP Analysis Set will be determined prior to study unblinding and will be detailed in the SAP.

#### **12.3.4. Safety Analysis Set**

All patients who are randomized and take at least 1 dose of randomized therapy will be included in the Safety Analysis Set. Safety analyses will be based on randomized therapy.

#### **12.3.5. Pharmacokinetic Analysis Set**

The PK Analysis Set includes all patients who have received at least 1 dose of study medication and have at least 1 confirmed, fasted, analyzable sample. Patients must have been fasting for approximately 8 hours before the visit and must not have any major protocol deviations that may potentially affect exposure levels. The PK Analysis Set will be used for PK analyses.

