Patients who discontinue study medication (at any point in the double-blind period) should continue in the double-blind period even if they permanently discontinue study medication and, if appropriate, will be encouraged to re-start study medication throughout the double-blind period at the Investigator's discretion (see [Section 6.3.1](#) and [Section 6.3.2](#)). However, if an End-of-Treatment (EOT)/early termination visit is completed during the double-blind period, study medication cannot be resumed. Dose titrations (up or down) are permitted at any time at the Investigator's discretion, and if appropriate, additional safety testing may be performed.

Throughout the study (including the open-label extension period), patients will be maintained on the maximum allowed dose of study medication they can tolerate while secondarily maintaining blood pressure as close as possible to the target of 125/75 mmHg. To maintain blood pressure, the Investigator will be encouraged to either treat patients with additional anti-hypertensive agents (with the exception of ACEIs, aldosterone blockers, aliskiren, ARBs, or ERAs) or withdraw anti-hypertensive agents. In the case of intolerable hypotension, withdrawal of additional anti-hypertensive agents should be accomplished before considering withdrawal or dose reduction of study medication. At the discretion of the Investigator, patients may reduce their dose in the double-blind period from 2 capsules/day to 1 capsule/day for safety or tolerability reasons.

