### 6.3.1. Temporary Interruption of Study Medication

Patients who temporarily interrupt study medication prior to completion of the study will continue with study visits and assessments according to the Schedules of Study Events (Section 15.1). Unless contraindicated, treatment should be resumed (titrated at the Investigator's discretion according to Section 8.3.2) whenever possible (including between visits) as long as an EOT/Early Termination (ET) visit is not completed.

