### **8.3.2. Dose Modification, Reduction, or Discontinuation**

Patients who display asymptomatic systolic blood pressure values  $\leq 100$  mmHg, diastolic blood pressure values  $\leq 60$  mmHg, or present with clinical symptoms of orthostatic hypotension but otherwise tolerate the initial sparsentan dose will continue after the Week 2 visit (or the Week 116 visit for the open-label extension period) without titrating up to the sparsentan target dose. Patients whose sparsentan dose is not titrated up to the target dose at Week 2 (or Week 116) may titrate up to that dose at any time based on evaluation of the Investigator in consultation with the Medical Monitor as needed.

The KDIGO Clinical Practice Guideline for Glomerulonephritis ([KDIGO 2012](#)) recommends a blood pressure target of  $<125/75$  mmHg when initial proteinuria is  $>1$  g/day. The KDIGO recommendation reflects standard-of-care in the United States (US) and all other participating countries. This is the basis for the 125/75 mmHg blood pressure target in the double-blind period, with the goal of attaining comparable blood pressure levels between treatment groups.

Throughout the study (including the open-label extension period), patients will be maintained on the maximum allowed dose of sparsentan they can tolerate while secondarily maintaining blood pressure as close as possible to the target of 125/75 mmHg. To maintain blood pressure, the Investigator will be encouraged to either treat patients with additional anti-hypertensive agents (with the exception of ACEIs, aldosterone blockers, aliskiren, ARBs, or ERAs) or withdraw anti-hypertensive agents. In the case of intolerable hypotension, withdrawal of additional anti-hypertensive agents should be accomplished before considering withdrawal or dose reduction of study medication. At the discretion of the Investigator, patients may reduce their study medication dose in the double-blind period from 2 capsules/day to 1 capsule/day for safety or tolerability reasons.

Sparsentan doses may be modified (either 200 mg or 400 mg) at any time throughout the open-label extension period for safety or tolerability reasons at the Investigator's discretion.

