## **4.2. Definition of Study Medication**

### **4.2.1. Double-Blind Period**

The investigational product doses to be administered in the double-blind period of the study will be dispensed as 200 mg sparsentan tablets over-encapsulated (blinded) with size 00 capsules. The active control doses to be administered in the double-blind period of the study will be dispensed as 150 mg irbesartan tablets over-encapsulated (blinded) with size 00 capsules.

The initial starting dose for study drug is 1 capsule (sparsentan 200 mg or irbesartan 150 mg). At the Week 2 visit, the Investigator will evaluate dose tolerance in a blinded manner prior to titrating up to the target dose of 2 capsules (sparsentan 400 mg or irbesartan 300 mg). Patients may continue on initial dose without titration or have dose reductions back to the initial dose (reduced dose) after dose titration based on tolerability as described in the protocol.

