## **9. PHARMACOKINETICS**

The PK Analysis Set will be used for all PK analyses. Trough plasma PK concentrations of study medication will be summarized at both the primary and final analyses with descriptive statistics over time by treatment group, including the geometric mean and geometric CV%. Analyte concentrations below the lower limit of quantification will be indicated by below limit of quantification (BLQ) and set to missing.

However, the number of BLQs at each time point will be provided in the summary table.

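### Trough concentrations are summarised by visit and arm only, so one-capsule and two-capsule samples are mixed and the average moves with the dose mix

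*Protocol*

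**What the plan says.** Protocol 6.1.2 lists trough plasma concentrations among the exploratory endpoints. Protocol 12.9.2 plans a descriptive summary at each visit. SAP section 9 says the troughs will be "summarized at both the primary and final analyses with descriptive statistics over time by treatment group", adds the geometric mean and geometric CV%, sets values below the quantification limit to missing, and reports how many there were. Neither section splits by dose taken or normalises to it.

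The PK Analysis Set (Protocol 12.3.5, repeated in SAP 6.3.5) consists of "patients who have received at least 1 dose of study medication and have at least 1 confirmed, fasted, analyzable sample". The same paragraph asks for a fast of about eight hours before the visit and for no major deviation that could affect exposure. SAP 7.3 applies its evaluability criteria to this set as well as to the per-protocol sets. Those criteria rule out extended gaps in dosing, and they judge compliance (80% to 120%) against the dose level that was prescribed.

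On dose, SAP 4.2.1 states: "The initial starting dose for study drug is 1 capsule (sparsentan 200 mg or irbesartan 150 mg"), followed after Week 2 by a "target dose of 2 capsules (sparsentan 400 mg or irbesartan 300 mg") if tolerated. The Protocol synopsis adds: "Dose titrations (up or down) are permitted at any time". Protocol 8.3.2 lets patients step down "from 2 capsules/day to 1 capsule/day for safety or tolerability reasons" and also lets those not titrated at Week 2 step up later. Protocol 6.3.1 adds: "Patients who temporarily interrupt study medication prior to completion of the study will continue with study visits and assessments". PK sampling stops only when an end-of-treatment visit has been completed (footnotes to Tables 15.1-1 and 15.1-2).

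**The concern.** A trough can be interpreted only with the dose that produced it. Within each arm the two allowed doses differ two-fold, and the planned average runs across both. A reader of the report could not attach the figure to either dose. Nor could they tell a change in pharmacokinetics between visits from a change in how many patients were on one capsule.

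This is the only drug-concentration summary planned for the double-blind period. It would be the natural place to look for exposure at the target dose or for stability of exposure over 110 weeks. No hypothesis test, sample size or claim of efficacy depends on it.

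**Working it through.** **Are both doses present when samples are drawn?** PK samples are scheduled at Weeks 6, 12 and 36 (Table 15.1-1) and at Weeks 48, 70, 94 and 110 (Table 15.1-2). All of these come after the Week 2 titration decision, so both dose levels can be present at every PK visit.

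**Does the analysis set remove one-capsule samples?** No. SAP 7.3 measures compliance against the prescribed dose level, so a patient reduced to one capsule who takes it is compliant. Nothing in Protocol 12.3.5 refers to the dose taken.

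**Size of the mixing.** The documents give no expected concentration, no share of patients at each dose and no ratio of troughs, so there is no plan figure to reproduce. Two inputs are assumed:

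- *f*: share of samples in the arm taken on one capsule.
- *r*: one-capsule trough divided by two-capsule trough. Dose proportionality would give *r* = 0.5.

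With target-dose geometric mean G, the pooled log mean is (1 − f)·log G + f·log(rG), so

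pooled geometric mean / target-dose geometric mean = r^f.

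For the arithmetic mean the ratio is 1 − f(1 − r).

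| f | r | Geometric ratio | Shortfall | Arithmetic ratio |
|---|---|---|---|---|
| 5% | 0.5 | 0.966 | 3.4% | 0.975 |
| 10% | 0.5 | 0.933 | 6.7% | 0.950 |
| 20% | 0.5 | 0.871 | 12.9% | 0.900 |
| 20% | 0.7 | 0.931 | 6.9% | 0.940 |
| 20% | 0.4 | 0.833 | 16.7% | 0.880 |

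**Apparent change between visits.** If f moves from f₁ to f₂ with pharmacokinetics unchanged, the pooled geometric mean is multiplied by r^(f₂ − f₁). With r = 0.5:

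- 10% to 30%: 0.5^0.2 = 0.871, an apparent fall of 12.9%.
- 20% to 20%: no change.
- 30% to 10%: 0.5^(−0.2) = 1.149, an apparent rise of 14.9%.

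The sign depends on how the dose mix moves, and the documents do not predict that.

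**Interruptions.** Visits continue during a temporary interruption, so some samples may be drawn off drug. Two rules limit their effect. Extended interruptions count against membership of the PK set (SAP 7.3), and unquantifiable values are set to missing, so they leave the mean. What can remain is a quantifiable sample from a shorter interruption. SAP 7.3 does not define how long an extended interruption is.

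**The case against.** The strongest reply is that little is at stake. The endpoint is exploratory and descriptive. SAP 10.2 already reports, by arm, time on the initial or reduced dose, time on the target dose, and reductions after titration, and patient listings are planned. A reader could judge the overall dose mix from these. That stands as a reason to rate the point low. It does not answer the point, because those tables give totals over the treatment period and not the mix at each PK visit.

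The magnitude also rests on assumed shares and an assumed trough ratio. That is correct. Only the two-fold dose difference comes from the documents, and at a 5% share the shortfall is 3.4%.

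A reader might infer several stronger points that the documents do not support:

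- **Troughs will appear to fall over the trial.** Up-titration is allowed at any time as well as reduction, so the direction is open.
- **The averages describe no real dose.** If few patients are on one capsule, the pooled value is close to the target-dose value.
- **Off-drug samples simply stay in and pull the mean down.** The evaluability criteria and the rule for unquantifiable values say otherwise, apart from the remainder noted above.
- **The fasting condition selects the wrong samples and should go.** The wording can be read as a condition on the patient or on each visit. The set also has an exposure-related deviation criterion, and nothing in the documents shows that fasting is irrelevant to these samples.

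**Conclusion.** The point holds in a limited form. The planned trough summaries pool two dose levels within each arm, and a prescribed reduction keeps the patient in the set, so the average shifts in either direction as the dose mix changes. On the assumption that half the dose gives half the trough, the pooled geometric mean is 3.4% to 13% below the target-dose value for one-capsule shares of 5% to 20%. At a 20% share it is about 7% to 17% below for trough ratios of 0.7 to 0.4. The shares and ratios are illustrations, not figures from the plan. A smaller residual issue is quantifiable samples from interruptions too short to count as extended. Severity is low: this is a cheap improvement to an exploratory summary, with no effect on the trial's efficacy conclusions.

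**What to change.** In SAP section 9, state that troughs will be summarised by visit, drug and actual daily dose at sampling (one or two capsules), with the dose taken from the dose log that SAP 10.2 already uses for compliance. Add that samples with no dose recorded on the previous day will be excluded from these summaries or flagged. The by-arm table can be kept alongside. The summary would still be by visit, as Protocol 12.9.2 requires, and the definition of the PK set can stay as it is.

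The cost is SAP wording and some programming from data already collected. The drawback is that one-capsule cells may be small at some visits; showing the number of samples in each cell deals with that.
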